8.2 Sample Size

Based on the initial data obtained to date and data in the literature ^[1], it is anticipated that approximately 50% of subjects hospitalized with PCR-positive SARS-CoV-2 infections

(WHO COVID-19 Classification level 3 or 4) will progress to WHO COVID-19 classification level of 6 or greater as defined by one or more of the following: the need for intubation or mechanical ventilation (level 6), the need for ECMO (level 7), or any cause death (level 8). The sample size estimate for this proof of concept is based on Fisher's Exact two-sided test for 2 proportions using NQuery 8 (www.statsols.com). Estimates of admitted patients requiring salvage therapy is unknown, however, the clinical data set who require intubation is a likely subset of those whose condition worsens but do not progress to respiratory compromise.

Although the interim analysis will utilize masked treatment assignments, the O'Brien Fleming group sequential sample size estimation confirms that a single interim look would retain a cumulative exit probability of 70% with a cumulative alpha =0.05 after the final analysis using the target enrollment of 132 (44 per group) to detect a reduction of those reaching the endpoint of treatment failure, which includes advancing to WHO COVID-19 Classification level \geq 6 from 50% (SOC treated) to 25% in either treatment group of SOC plus GLS-1027. Other conditions also qualify a subject as treatment failure include: need for salvage therapy with IL-6 monoclonal antibody; or institution of salvage therapy with dexamethasone (\geq 6 mg/day), withdrawing consent from the study, becoming lost to follow-up, or discontinuation of treatment for any reason other than renal function or pregnancy. This study is not powered to assess statistically significant differences between GLS-1027 doses.

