4. DETERMINATION OF SAMPLE SIZE

Based on the initial data obtained to date and data in the literature, it is anticipated that approximately 50% of subjects hospitalized with PCR-positive SARS-CoV-2 infections (WHO COVID-19 Classification level 3 or 4) will experience treatment failure at day 28 from enrollment. Treatment failure is defined as progression to WHO COVID-19 classification level of 6 or greater as defined by one or more of the following: the need for high-flow oxygen or non-invasive ventilation, the need for intubation or mechanical ventilation (level 6), the need for ECMO (level 7), or any cause death (level 8); the initiation of a non-study immune modulator; withdrawing consent from the study; becoming lost to follow-up; or discontinuation of treatment for any reason other than renal function or pregnancy. The sample size estimate for this proof of concept is based on Fisher's Exact two-sided test for 2 proportions using NQuery 8 (www.statsols.com). Estimates of admitted patients requiring salvage therapy is unknown, however, the clinical data set who require intubation is a likely subset of those whose condition worsens but do not progress to respiratory compromise.

Although the interim analysis will utilize masked treatment assignments, the O'Brien Fleming group sequential sample size estimation confirms that a single interim look would retain a cumulative exit probability of 70% with a cumulative alpha =0.05 after the final analysis using the target enrollment of 132 (44 per group) to detect a reduction of those reaching the endpoint of treatment failure. This study is not powered to assess statistically significant differences between GLS-1027 doses. A gate-keeping method will be used to compare the highest dose to placebo first and then compare the lower dose if the higher dose shows significant benefit.

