8.2. Analysis of the Primary Efficacy Endpoint

The proportion of subjects in each treatment group who reach the study endpoint of treatment failure by 28 days will be compared to placebo using Fisher's Exact 2-sided test of proportions. Additionally, the frequency for each outcome (intubation, ECMO, death) will be determined within each group. The ITT, mITT and PP analysis populations will be used to analyze the primary endpoint.

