Treatment Failure [1]	x (xx.x%)	x (xx.x%)	x (xx.x%)	
Achieved WHO level >=6	x (xx.x%)	x (xx.x%)	x (xx.x%)	
Lost to follow-up	x (xx.x%)	x (xx.x%)	x (xx.x%)	
Withdrawal of informed consent	x (xx.x%)	x (xx.x%)	x (xx.x%)	
Required salvage therapy	x (xx.x%)	x (xx.x%)	x (xx.x%)	
Discontinued study drug prior to discharge	x (xx.x%)	x (xx.x%)	x (xx.x%)	
Had missing assessment of WHO level classification	x (xx.x%)	x (xx.x%)	x (xx.x%)	
p-value [2]	0.xxxx	0.xxxx	, ,	
Maximum WHO Level = 6 (Intubation or Mechanical Ventilation)	x (xx.x%)	x (xx.x%)	x (xx.x%)	
Maximum WHO Level = 7 (Requirement for ECMO)	x (xx.x%)	x (xx.x%)	x (xx.x%)	
Maximum WHO Level = 8 (Death)	x (xx.x%)	x (xx.x%)	x (xx.x%)	

^[1] Subjects who met any of the reasons listed are considered treatment failures. Subjects who failed treatment for multiple reasons are counted once for each reason.

Reference: Listing 16.2.6.1

Programming note: Repeat for Table 14.2.1.2 Analysis of Overall Treatment Failure (mITT Population).

Programming note: Repeat for Table 14.2.1.3 Analysis of Overall Treatment Failure (PP Population).

Programming note: P-values will not be provided for corticosteroid use/non-use subset pages.

^[2] P-value is calculated using a Fisher's exact test and compares the active treatment to placebo. Will only be provided for the 120 mg group if the 360 mg group is significant.

GeneOne Life Science Inc.

Page 1 of 1

Protocol: GLS27-005

Table 14.2.2.1.1

Summary of the Number of Days Requiring ICU Care
(ITT Population)

	GLS-1027	GLS-1027	Placebo
	120 mg	360 mg	(N=XX)
	(N=XX)	(N=XX)	, ,
umber of Days Requiring ICU Care			
n	X	X	Х
Mean (SD)	xx.xx (xx.xxx)	xx.xx (xx.xxx)	xx.xx (xx.xxx)
Median	x.xx	x.xx	x.xx
nearan			xx.x, xx.x

Reference: Listing xxxxx

Programming note: Repeat for Table 14.2.2.1.2 Summary of the Number of Days Requiring ICU Care (PP Population).

Protocol: GLS27-005

Table 14.2.2.2.1

Summary of the Number of Days on Mechanical Ventilation
(ITT Population)

	GLS-1027	GLS-1027	Placebo
	120 mg	360 mg	(N=XX)
	(N=XX)	(N=XX)	, ,
umber of Days on Mechanical Ventilation			
umber of Days on Mechanical Ventilation n	х	x	×
	x xx.xx (xx.xxx)	x xx.xx (xx.xxx)	x xx.xx (xx.xxx)
n			

Reference: Listing 16.2.6.2

Programming note: Repeat for Table 14.2.2.2.2 Summary of the Number of Days on Mechanical Ventilation (PP Population).

Protocol: GLS27-005

Table 14.2.2.3.1 Summary of the Number of Days Requiring Nasal Oxygen (O_2) Administration (ITT Population)

	GLS-1027	GLS-1027	Placebo

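### The plan's single 70% power figure does not hold for 120 mg under the SAP's testing order: about 56% if the 70% is accepted, 45% with the planned Fisher test

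*SAP*

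**What the plan says.** Protocol 8.2, repeated in the synopsis, states a 70% chance of detecting a reduction "from 50% (SOC treated) to 25% in either treatment group of SOC plus GLS-1027". It sets no order of testing between the doses.

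SAP 4 carries over the design figure, with 132 patients in all and 44 in each arm: a "single interim look would retain a cumulative exit probability of 70% with a cumulative alpha =0.05 after the final analysis". It repeats the 50% placebo rate but gives no active-arm rate and does not say which dose the 70% describes. It then adds the order: "A gate-keeping method will be used to compare the highest dose to placebo first and then compare the lower dose if the higher" one succeeds. The shell for Table 14.2.1.1 in SAP Appendix C puts this into effect. Its footnote on the p-value reads "Will only be provided for the 120 mg group if the 360 mg group is significant".

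On the test, SAP 4 says "The sample size estimate for this proof of concept is based on Fisher's Exact two-sided test for 2 proportions", and SAP 8.2 says each dose "will be compared to placebo using Fisher's Exact 2-sided test of proportions". Neither document gives a power for 120 mg under the testing order.

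**The concern.** In a fixed sequence, the second dose can be declared effective only if the first dose also succeeds. Its power is therefore the joint probability of two successes. That cannot exceed its ungated power, and it equals the ungated power only if the first dose is certain to succeed. One unqualified 70% beside the gate invites the reader to apply it to both doses.

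At stake is how a 120 mg result without a p-value is read. Someone who believes 120 mg had a 70% chance of a formal claim may take the absence of one as evidence against the dose, when the chance was much lower and depended on how 360 mg performed.

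**Working it through.** **Inputs.** 44 per group and two-sided alpha 0.05 (SAP 4); placebo failure rate 50% (SAP 4 and Protocol 8.2); 25% in each active arm (Protocol 8.2 only); Fisher's exact two-sided test (SAP 4 and 8.2); 360 mg tested first, then 120 mg (SAP 4, Table 14.2.1.1 footnote).

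**Step 1: the plan's own figure.** For one ungated comparison by the normal formula with unpooled variance:

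- SE = √[(0.50×0.50 + 0.25×0.75)/44] = √(0.4375/44) = 0.0997
- 0.25/0.0997 − 1.960 = 0.547, and Φ(0.547) = 70.8%

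Other z-type calculations agree: 70.4% for a two-look O'Brien-Fleming design with unpooled variance, and 70.1% for the pooled z test by exact binomial enumeration. So 70% is a reasonable figure for one ungated z-type comparison. Fisher's exact test, enumerated in the same way, gives 61.1%.

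**Step 2: power for 120 mg through the gate.** Let R(x; p) be the probability that a dose with true failure rate p is significantly better than placebo when x of 44 placebo patients fail. Both comparisons use the same x, so

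P(120 mg declared effective) = Σₓ Bin(x; 44, 0.50) × R(x; p₃₆₀) × R(x; p₁₂₀), for x = 0 to 44.

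This is exact and allows for the shared placebo arm. Squaring the single-comparison power would be too pessimistic (37.3% for Fisher, 49.1% for pooled z), because a shared control makes the two results positively correlated.

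**Step 3: results at 50/25/25.**

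| | 360 mg v placebo | 120 mg through the gate | 120 mg given 360 mg significant |
|---|---|---|---|
| Pooled z | 70.1% | 55.7% | 79.5% |
| Fisher exact | 61.1% | 44.9% | 73.5% |

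Other z-type variants put the gated figure between about 53% and 59%. A simulated two-look pooled z design gives 68.9% for one comparison and 54.0% gated. Lowering the final Fisher level to 0.049, to allow for an O'Brien-Fleming type look, leaves 61.1% and 44.9% unchanged.

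**Step 4: how much is due to the gate.** With the test held fixed, the gate costs 70.1 − 55.7 = 14.4 points (pooled z) or 61.1 − 44.9 = 16.2 points (Fisher). The step from 70.1% to 61.1%, 9.0 points, comes from the choice of test and has nothing to do with the gate.

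**Step 5: dependence on 360 mg.** 120 mg is held at 25% and placebo at 50%:

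| True 360 mg failure rate | 120 mg gated, Fisher | 120 mg gated, pooled z |
|---|---|---|
| 15% | 59.7% | 69.0% |
| 20% | 54.9% | 65.1% |
| 25% | 44.9% | 55.7% |
| 30% | 31.3% | 41.2% |
| 35% | 18.2% | 25.7% |

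As the 360 mg effect grows, the 120 mg figure approaches its ungated value (61.1% or 70.1%) and cannot pass it.

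**The case against.** The best defence is that each document is coherent alone. The protocol states power for a pairwise comparison and has no gate. The SAP has the gate but does not repeat the 25% rate or the wording that extends the figure to either arm. Quoting power for the first hypothesis in a sequence is ordinary practice. This stands as to location: the contradiction appears when the two documents are read together. It does not rescue the figure, because SAP 4 puts one unlabelled 70% next to the gate.

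Two other defences do not help. If 'either' means at least one dose, gated power is that of 360 mg alone, and 120 mg still has no stated power. The statement that the study is not powered to compare doses concerns dose against dose, not 120 mg against placebo.

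Some stronger readings are tempting but unsupported:

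- *The gate alone takes 70% to 45%.* It does not; about 9 points of that fall come from Fisher against a z-type test.
- *The sponsor added the gate and failed to recalculate.* The documents give neither the history nor the method behind the 70%. The SAP cites Protocol version 5.0, and the protocol text available differs from the SAP in treatment period (28 v 14 days) and in the failure definition. The cited version may word its power statement differently.
- *360 mg is likely to do worse because stopping treatment counts as failure.* Protocol 1.4 describes the doses as within those already tolerated, and SAP 8.1 exempts listed temporary stops. Stronger and weaker 360 mg effects should therefore both be shown.
- *The 120 mg result will be missing, or the DSMB will be misled.* Table 14.2.1.1 shows the 120 mg counts and percentages regardless; only the p-value is withheld, and a footnote says so. The interim review is a masked safety review with no futility stop.

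**Conclusion.** The point holds. Under the SAP's testing order the 70% does not apply to 120 mg. If the single-comparison 70% is accepted, the gate lowers 120 mg to about 56%. With the test the plan names, the figures are 61% for 360 mg and 45% for 120 mg.

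These rest on 44 evaluable per arm, true failure rates of 50%, 25% and 25%, significance counted only in the direction of benefit, and no efficacy stop at the interim. The 25% rate comes from the protocol alone.

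A reader might infer that the gate is a flaw or that the trial is too small. Neither follows: the gate is a valid way to control type I error, and this is a proof-of-concept study. The defect is confined to the power statement.

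**What to change.** In SAP 4:

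- State the 25% active-arm rate and say that the power figure is for 360 mg against placebo: 61% with Fisher's exact test at 50% v 25%, 44 per group.
- Add the power for 120 mg through the gate: 45% with Fisher at 50/25/25.
- Add the range with 120 mg held at 25% (Fisher): 60%, 55%, 31% and 18% for true 360 mg failure rates of 15%, 20%, 30% and 35%.

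In Protocol 8.2 and the synopsis, after checking the protocol version that the SAP cites, replace the wording that applies the figure to either active arm with a statement that it refers to a single ungated comparison.

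The gate, sample size and conduct stay as they are. The only cost is a less favourable stated power.

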5. GENERAL ANALYSIS CONSIDERATIONS

The statistical analysis results will be reported using tables, listings, and figures (TLFs). Summaries of continuous variables will display means, standard deviations (SDs), medians, minimums, maximums, and the number of observations. Summaries of categorical variables will display frequency counts and percentages.

CONFIDENTIAL Page 8 03DEC2021

^h Record maximal daily level of PEEP and delivered FiO2 by mechanical ventilation, if participant is receiving mechanical ventilation

All analyses will be performed using SAS® Version 9.4 or higher.

A masked interim analysis will be performed when 22 subjects in each group have been assessed for the primary endpoint of treatment failure. The primary goals of this analysis are to review blinded safety to ensure that GLS-1027 has no concerns or causes worsening conditions. Unless safety is of concern, the study will not be stopped for futility and enrollment will continue to the targeted sample size of 132.

6. ANALYSIS POPULATIONS

6.1. Intent-to-treat (ITT) Population

The ITT Population will include all subjects randomized to a treatment allocation. The ITT population will be used for the summary of all demographic and baseline characteristics and for analysis of the primary outcome of treatment failure. Subjects will be grouped in analyses and summaries based on their randomization allocation.

6.2. Modified Intent-to-treat (mITT) Population

The modified intention to treatment (mITT) population includes all participants who are randomized to a treatment allocation, and who have received at least one dose of study drug. The mITT population will be used for the summary and analysis of the primary outcome of treatment failure. Participants will be grouped based on the treatment allocation.

6.3. Safety Population

The Safety Population will include all participants in the mITT population. Subjects will be grouped in analyses and summaries based on their actual treatment.

6.4. Per-protocol (PP) Population

The PP Population includes all safety subjects who complete the trial by meeting the endpoint of treatment failure or being discharged within 14 days without meeting the endpoint. Subjects will be grouped in analyses and summaries based on their actual treatment. This set will be used as a sensitivity analysis to summarize the primary and other efficacy outcomes.

7. STUDY POPULATION

7.1. Subject Disposition

The number and percentage of subjects who were screened and failed screening, who were in each analysis population, who completed the study and who discontinued prior to study completion will be presented by treatment group (GLS-1027 120 mg, GLS-1027 360 mg, and placebo) and overall. Subjects who discontinued prior to completing the study will also be summarized by reason for discontinuation.

Subject disposition will also be listed.

CONFIDENTIAL Page 9 03DEC2021

7.2. Protocol Deviations

Protocol deviations with significance will be listed.

7.3. Demographics and Baseline Characteristics

Demographics and baseline data, vital signs, medical history, prior and concomitant medications, and treatments will be summarized by means of descriptive statistics: continuous variables as mean, median, SD, minimum/maximum ranges and categorical variables as frequencies and percentages, grouped by treatment arms and overall, based on ITT population. Demographic and baseline characteristics will also be listed.

7.4. Medical History

Medical history verbatim terms collected from the CRF will be mapped to system organ classes (SOCs) and preferred terms (PTs) using the Medical Dictionary for Regulatory Activities (MedDRA) (version 23.0).

Summaries (number and percentage of subjects) of medical history by SOC and PT will be provided by treatment and overall.

A listing of medical history will also be provided.

7.5. Prior and Concomitant Medications

A prior medication is defined as a medication that was administered up to 4 months prior to time of enrollment. All other medications will be considered concomitant.

Medication verbatim names collected from the CRF will be mapped to Anatomical Therapeutic Chemical (ATC) Classes and Preferred Names using the World Health Organization's WHODrug Global March 2020 version. Preferred Names will consist of only the base compounds and not the salts (e.g., Naproxen Sodium will be listed only as Naproxen). Concomitant medications will be summarized for each treatment by ATC class and preferred name. Prior and concomitant medications will be listed.

7.6. Study Drug Exposure

Exposure summaries of duration of exposure, total number of doses taken, and total number of doses missed will be provided by treatment. Duration of exposure is defined as the date of last dose minus the date of first dose + 1, regardless of if any doses were missed in between. Exposure data will be listed.

7.7. Blood Collection for Pharmacokinetic and PBMC Results

Blood collection information (date/time and volume of blood) for PK assessments, trough drug measurements, serum, and PBMCs will be listed.

CONFIDENTIAL Page 10 03DEC2021

8. EFFICACY ANALYSES

8.1. Definition of the Primary Efficacy Endpoint

The primary endpoint is treatment failure within 28 days of enrollment. Treatment failure is defined as:

- Progression to WHO classification level 6 or greater including the need for high-flow oxygen or non-invasive ventilation
- Receiving salvage therapy with a non-study immune-modulator (Appendix A).
- Lost to follow-up through hospital transfer, within the 14-day primary treatment period.
- Discontinuation of study drug for any cause prior to day 14 or hospital discharge will be considered as a treatment failure, except for those for whom study drug was temporarily suspended due to a decrease in renal function (creatinine clearance of < 60 mL/min), other reasons for temporary cessation of treatment listed in Section 7.3.2 of the protocol, or for discontinuation in the case of pregnancy. These subjects will be followed for the primary endpoint at 28 days with long-term follow-up at day 56.

Subjects who complete 14 days of treatment but remain hospitalized but do not meet the criteria for treatment failure, will not considered be as treatment failures with respect to the primary endpoint.

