2.2. Exploratory Objectives

The exploratory objectives are:

- Assess the number of days requiring ICU care relative to treatment group.
- Assess the number of days of NIV, high-flow O2 or mechanical ventilation relative to treatment group.
- Assess incidence of WHO COVID-19 Classification levels relative to baseline serum IL-6 level.
- Assess incidence of WHO COVID-19 Classification levels relative to baseline serum ferritin level.
- Assess incidence of WHO COVID-19 Classification levels relative to baseline CRP
- Assess trough level of GLS-1027 relative to serum creatinine.
- Assess the maximal level of Positive End-Expiratory Pressure (PEEP) for subjects who are intubated relative to treatment group.
- Assess the number of days of PEEP > 5 cm H2O for subjects who are intubated relative to treatment group.
- Assess change in WHO COVID-19 Classification level at Day 28 from enrollment, relative to group.
- Assess SARS-CoV-2 IgM antibody responses relative to treatment group.

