	GLS-1027	GLS-1027	Placebo
	120 mg	360 mg	(N=XX)
	(N=XX)	(N=XX)	· · ·
umber of Days in Hospital			
n	X	x	x
Mean (SD)	xx.xx (xx.xxx)	xx.xx (xx.xxx)	xx.xx (xx.xxx)
Median	x.xx	x.xx	x.xx
Min, Max	xx.x, xx.x	xx.x, xx.x	xx.x, xx.x

Reference: Listing xxxxx

Programming note: Repeat for Table 14.2.2.8.2 Summary of the Number of Days in Hospital (PP Population).

Table 14.2.3.1

Cumulative Incidence of SARS-CoV-2 IgM Antibody Response by Study Day

(PP Population)

Study Day	GLS-1027	GLS-1027	Placebo
Responded	120 mg	120 mg	(N=XX)
	(N=XX)	(N=XX)	`n(%)´
	,	· · · · · · · · · · · · · · · · · · ·	
Day 1			
n	X	X	X
Yes	x (xx.x%)	x (xx.x%)	x (xx.x%)
No	x (xx.x%)	x (xx.x%)	x (xx.x%)
Day 2			
n	X	x	Х
Yes	x (xx.x%)	x (xx.x%)	x (xx.x%)
No	x (xx.x%)	x (xx.x%)	x (xx.x%)
Day 3			
n	X	X	X
Yes	x (xx.x%)	x (xx.x%)	x (xx.x%)
No	x (xx.x%)	x (xx.x%)	x (xx.x%)
Day 4			
n	X	X	X
Yes	x (xx.x%)	x (xx.x%)	x (xx.x%)
No	x (xx.x%)	x (xx.x%)	x (xx.x%)
	(,	~ ()	. (,
••			

The incidence of antibody response is summarized based on results obtained at or prior to the study day. Reference: Listing 16.2.6.3

Table 14.2.4.1
WHO COVID-19 Classification Levels Relative to Baseline Serum Ferritin Level
(PP Population)

			GL	S-1027			GLS-1027								
				L20 mg			360 mg			Placebo			0verall		
WHO Classification	(N=XX)						(N=XX)			(N=XX)		(N=XX)			
Level	Serum Ferritin [1]	Post-Baseline					Post-Baseline			Post-Baseline			Post-Baseline		
	Baseline	Low	N	lormal	High	Low	Normal	High	Low	Normal	High	Low	Normal	High	
5	n	х		х	x	x	х	х	х	х	x	x	х	х	
	Low					XX	XX	XX	XX	XX	XX	XX	XX	XX	
		xx (xx	.x) xx	(xx.x) xx	(xx.x)	(xx.x)	(xx.x)	(xx.x)	(xx.x)	(xx.x)	(xx.x)	(xx.x)	(xx.x)	(xx.)	
	Normal					XX	XX	XX	XX	XX	XX	XX	XX	XX	
		xx (xx	.x) xx	(xx.x) xx	(xx.x)	(xx.x)	(xx.x)	(xx.x)	(xx.x)	(xx.x)	(xx.x)	(xx.x)	(xx.x)	(xx.	
	High					XX	XX	XX	XX	XX	XX	XX	XX	XX	
		xx (xx	.x) xx	(xx.x) xx	(xx.x)	(xx.x)	(xx.x)	(xx.x)	(xx.x)	(xx.x)	(xx.x)	(xx.x)	(xx.x)	(xx.	
6	n	х		х	x	x	х	х	х	х	x	x	х	х	
	Low					XX	XX	XX	XX	XX	XX	XX	XX	XX	
		xx (xx	.x) xx	(xx.x) xx	(xx.x)	(xx.x)	(xx.x)	(xx.x)	(xx.x)	(xx.x)	(xx.x)	(xx.x)	(xx.x)	(xx.	
	Normal					XX	XX	XX	XX	XX	XX	XX	XX	XX	
		xx (xx	.x) xx	(xx.x) xx	(xx.x)	(xx.x)	(xx.x)	(xx.x)	(xx.x)	(xx.x)	(xx.x)	(xx.x)	(xx.x)	(xx.	
	High					XX	XX	XX	XX	XX	XX	XX	XX	XX	
		xx (xx	.x) xx	(xx.x) xx	(xx.x)	(xx.x)	(xx.x)	(xx.x)	(xx.x)	(xx.x)	(xx.x)	(xx.x)	(xx.x)	(xx.	
7	n	х		х	x	x	x	х	х	х	x	x	х	х	
	Low					XX	XX	XX	XX	XX	XX	XX	xx	XX	

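### The SAP text counts high-flow oxygen or non-invasive ventilation as primary failure within WHO level 6 or greater, but the primary table labels level 6 as intubation and has no row for it

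*SAP*

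**What the plan says.** **Text that counts high-flow oxygen or NIV as failure**

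- SAP 8.1, first criterion: "Progression to WHO classification level 6 or greater including the need for high-flow oxygen or non-invasive ventilation".
- SAP 4 defines failure as level 6 or greater and then lists "the need for high-flow oxygen or non-invasive ventilation, the need for intubation or mechanical ventilation (level 6), the need for ECMO (level 7"), followed by death as level 8. High-flow/NIV is the only item in that list without a level number.

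**Parts of the SAP that do not fit**

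- SAP 8.2: "Additionally, the frequency for each outcome (intubation, ECMO, death) will be determined within each group". High-flow/NIV is not among the outcomes named.
- SAP Appendix C, Table 14.2.1.1: the progression row reads "Achieved WHO level >=6". The other reasons are loss to follow-up, withdrawal of consent, salvage therapy, stopping study drug before discharge, and a missing WHO assessment. A footnote makes a failure of anyone who meets at least one listed reason. Below the p-value come rows for maximum level 6, 7 and 8, the first being "Maximum WHO Level = 6 (Intubation or Mechanical Ventilation"). The only source cited is Listing 16.2.6.1, which holds the numeric WHO level.
- SAP Appendix C, Table 14.2.4.1 ("WHO COVID-19 Classification Levels Relative to Baseline Serum Ferritin Level") and its IL-6 and CRP counterparts show level 5 as a block separate from level 6.

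**Protocol.** The WHO scale in the appendices scores NIV or high-flow oxygen as 5 and intubation as 6, and exclusion criterion 11 agrees. Protocol 8.6 limits level 6 or greater to intubation with ventilation, ECMO or death.

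**The concern.** This decides who counts as a failure on the primary efficacy endpoint. Patients enter at level 3 or 4, so on the protocol's scale level 5 is the next step of worsening above level 4. If the table is programmed as level 6 or greater from the numeric listing, patients whom SAP 8.1 counts as failures are dropped. If they are placed in that row anyway, they fit none of the three maximum-level rows beneath it.

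The choice would then be made at programming. The SAP tests 120 mg only if 360 mg is significant, so a change in the 360 mg result carries over to the second comparison.

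The 50% control rate is also affected. SAP 4 attaches it to a failure definition that includes high-flow/NIV. Protocol 8.2 attaches it to the share who "will progress to WHO COVID-19 classification level of 6 or greater as defined by one or more of the following": intubation or ventilation, ECMO, or death.

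**Working it through.** **1. Same patient, two rules.** Take a patient whose worst state is high-flow oxygen or NIV and who meets no other listed reason.

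- SAP 8.1 and SAP 4: failure.
- Table 14.2.1.1 as labelled: level 6 means intubation or ventilation and no listed reason applies, so not a failure.

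A patient who also meets another listed reason is a failure under both rules.

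**2. The plan's own power figure.** Inputs: 44 per group, two-sided alpha 0.05 and one O'Brien-Fleming look at 22 per group (SAP 4 and 5); 50% v 25% (the 25% is in Protocol 8.2 only).

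- Standard error = √(0.5×0.5/44 + 0.25×0.75/44) = 0.0997
- Final-look drift = 0.25/0.0997 = 2.507; half-way drift = 2.507×√0.5 = 1.773
- Power = 1 − P(Z1 < 2.797, Z2 < 1.977), with correlation √0.5, = 70.4%

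This reproduces the stated 70%. The two-sided Fisher test that the SAP specifies, by exact enumeration with no interim look (reject if p ≤ 0.05), has 61.1% power. That gap is a separate matter; the Fisher figure is the reference below because Fisher is the planned test.

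**3. Fisher p-values near the planned result** (placebo v active failures, 44 per arm)

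| Counts | Change from 22 v 11 | p |
|---|---|---|
| 22 v 11 | none | 0.027 |
| 21 v 11 | 1 placebo removed | 0.045 |
| 20 v 11 | 2 placebo removed | 0.073 |
| 22 v 12 | 1 active added | 0.048 |
| 22 v 13 | 2 active added | 0.081 |
| 20 v 10 | 2 and 1 removed | 0.042 |
| 18 v 9 | 4 and 2 removed | 0.063 |
| 24 v 13 | 2 added to each | 0.030 |
| 26 v 15 | 4 added to each | 0.032 |

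**4. Fisher power under assumed rates.** The documents give no rate for patients whose only failure reason is high-flow/NIV. Assume 5, 10 or 20 percentage points of the placebo arm (0.05×44 = 2.2, 0.10×44 = 4.4, 0.20×44 = 8.8 patients). The reference is 50 v 25%, 61%.

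| Scenario | 5 points | 10 points | 20 points |
|---|---|---|---|
| (a) 50 v 25% includes them; table drops them, halving kept | 45 v 22.5%: 53% | 40 v 20%: 45% | 30 v 15%: 29% |
| (b) 50 v 25% is level 6 or greater; text adds them, halving kept | 55 v 27.5%: 68% | 60 v 30%: 74% | 70 v 35%: 87% |
| (c) as (b), no drug effect on those added | 55 v 30%: 57% | 60 v 35%: 55% | 70 v 45%: 57% |

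If the table drops equal numbers from both arms, power rises: 45 v 20% gives 64% and 40 v 15% gives 68%. The effect can thus go either way. Overlap with other failure reasons shrinks every shift.

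**The case against.** The two SAP sections that define failure agree that high-flow/NIV counts. On this view the table's progression row is shorthand for the first criterion of SAP 8.1, the maximum-level rows are descriptive, SAP 8.2 only adds a supplementary tabulation, and Appendices A and B allow tables to be reorganised during programming. The gap would then be a defect in a shell, not a second endpoint. The shorthand reading is possible, but nothing in the SAP establishes it. The text itself places high-flow/NIV under a level that SAP 4 labels intubation, and freedom over layout does not extend to who counts as a failure.

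Some of the objection stands:

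- SAP 8.2 also omits salvage therapy and discontinuation, so its silence on high-flow/NIV is weak evidence by itself.
- The SAP prints no WHO scale. The score of 5 comes from the supplied protocol, which has 28 days of treatment against the SAP's 14 and so appears not to be the version 5.0 that the SAP cites. The scale is supporting evidence only; the clash between SAP 8.1 and the table's label for level 6 does not need it.
- The p-values that cross 0.05 with two patients put both in one arm. They show what can happen, not what is likely.
- Protocol 8.2 also describes the fall from 50% to 25% as a fall in treatment failure that includes level 6 or greater, so scenario (b) is one reading of it.

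**Conclusion.** The concern holds. The SAP does not fix whether a patient whose only event is high-flow oxygen or NIV is a primary failure, and this must be settled before unblinding. The conflict is read directly from the SAP; the size is not known. If two patients in one arm are reclassified, the planned result can move from p = 0.027 to 0.073 or 0.081, while several more balanced shifts leave it below 0.05. Power runs from 29% to 87% across scenarios (a) to (c), against 61% at 50 v 25%. Those figures rest on assumed rates of 5 to 20 points, on the 25% taken from the protocol, and on no overlap with other failure reasons.

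**What to change.** Before unblinding, reconcile SAP 4, 8.1, 8.2 and Table 14.2.1.1 to one definition.

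- **If high-flow/NIV counts:** make it a separate criterion outside level 6 or greater. Add a failure-reason row and a maximum-level-5 row to Table 14.2.1.1 and its mITT and PP repeats, after confirming the level against the scale in protocol version 5.0. The exploratory objective "Assess the number of days of NIV, high-flow O2 or mechanical ventilation relative to treatment group" shows that this form of support is already of interest, but it does not settle the endpoint.
- **If it does not count:** delete the phrase from SAP 4 and 8.1.
- **Either way:** state which definition the 50% control rate describes. Reporting the other definition as a sensitivity analysis would be useful but is secondary.

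The cost is wording in three SAP sections and one table shell with its repeats. If high-flow/NIV counts, there is also a data-capture question. SAP Table 1 records WHO level on Days 1 to 15, 28 and 56, and CPAP, ventilator and ECMO use only to Day 15. A short episode on Days 16 to 27 would depend on the Day 28 record review. The SAP should say that this review looks for such episodes, or acknowledge that they may be missed.
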